An interim analysis is planned after all participants receiving SC administration in Part 1 complete their Week 24 visit. At that time point, the data available for participants receiving IV administration will also be analyzed and included.

Brief Summary:

The purpose of this study is to assess the safety, tolerability, and PK of a single 20 mg/kg or **CCI** [REDACTED] or a single 60 mg/kg IV dose of GSK3810109, in healthy adult participants.

- Study duration: Up to 24 weeks excluding screening
- Treatment duration:
 - For Part 1, single SC infusion on Day 1 that is expected to take 3 to 15 minutes to administer.
 - For Part 2, single IV infusion on Day 1, that is expected to take approximately 60 minutes to administer; the entire infusion should not exceed 2 hours.
 - **CCI** [REDACTED]

Number of Participants:

A sufficient number of participants will be enrolled to ensure that approximately 8 participants complete each part of the study for a total of approximately 24 participants in the study.

Participants who withdraw prior to study completion may be replaced.

Note: Enrolled means a participant's agreement to participate in a clinical study following completion of the informed consent process and all screening activities. Potential participants who are screened for the purpose of determining eligibility for the study, but do not participate in the study, are not considered enrolled. A participant will be considered enrolled if the informed consent is not withdrawn prior to participating in any study activity after screening.

Intervention Groups and Duration:

The study duration will be 24 weeks (excluding screening) and the study product will be administered on Day 1 of each part.

Data Monitoring/ Other Committee: No Data and Safety Monitoring Board will be empaneled for this study

[figure not shown]
An SRT for GSK3810109 reviews emerging and cumulative data for GSK3810109 on a monthly basis. For Part 1, safety review decisions and the status of the enrollment process will be shared with an SRT at regular intervals and discussed during the monthly SRT meetings.

For Part 2, a core SRT for Study 217901 will review data for both sentinel and non-sentinel participants of the study. [CC1]

[REDACTED] The core SRT is composed of safety lead, medical monitors, and project biostatistician.

[figure not shown]

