1.6. Schedule of Activities (SoA) (Part 2)

| Visit Number | | | 01 | 01A | 01B | 01C | 02 | 03 | 04 | 05 | 06 | 07 | 08 | 09 | 10 | 11 | 12 | 13 | 14 | 15 | ED = early discontinuation/withdrawal |
|--------------------------------------------------------|--------------------------|----------|---------------------|-----|-----|-----|------|------|------|-----|-----|------------------|-----|-----|-----------|-----|------|------|------|------|---------------------------------------|
| Time From Start of IV Infusion | | | Pre | EOI | 4hr | 8hr | 24hr | 48hr | 72hr | Wk1 | Wk2 | Wk2 | Wk2 | Wk3 | Wk4 | Wk8 | Wk12 | Wk16 | Wk20 | Wk24 | |
| Day of Study ¹ | | D-1 | D1 | D1 | D1 | D1 | D2 | D3 | D4 | D7 | D8 | D10 ² | D14 | D21 | D28 | D56 | D84 | D112 | D140 | D168 | |
| Clinical Activity | Screen Days -21 to -2 | Check-in | Intervention Period | | | | | | | | | | | | Follow-up | | | | | | |
| Informed consent | X | | | | | | | | | | | | | | | | | | | | |
| Admission to clinic | | X | | | | | | | | | | | | | | | | | | | |
| Discharge from clinic | | | | | | | | | | | X | | | | | | | | | | |
| Inclusion and exclusion criteria | X | X | | | | | | | | | | | | | | | | | | | |
| Demographics | X | | | | | | | | | | | | | | | | | | | | |
| Height, weight, and BMI ³ | X | X | X | | | | | | | | | | | | | | | | | | |
| Vital signs ⁴ | X | X | X | | X | X | X | X | X | X | X | X | X | X | X | X | X | X | X | X | |
| Physical examination ⁵ | X | X | X | X | | X | | | | | | X | | | | | | | | X | |
| Drug Alcohol/Cotinine /history and screen ⁶ | X | X | | | | | | | | | | | | | | | | | | | |

| Visit Number | | | 01 | 01A | 01B | 01C | 02 | 03 | 04 | 05 | 06 | 07 | 08 | 09 | 10 | 11 | 12 | 13 | 14 | 15 | ED = early discontinuation/withdrawal |
|-----------------------------------------------------|--------------------------|----------|---------------------|-----|-----|-----|------|------|------|-----|-----|------------------|-----|-----|-----------|-----|------|------|------|------|---------------------------------------|
| Time From Start of IV Infusion | | | Pre | EOI | 4hr | 8hr | 24hr | 48hr | 72hr | Wk1 | Wk2 | Wk2 | Wk2 | Wk3 | Wk4 | Wk8 | Wk12 | Wk16 | Wk20 | Wk24 | |
| Day of Study ¹ | | D-1 | D1 | D1 | D1 | D1 | D2 | D3 | D4 | D7 | D8 | D10 ² | D14 | D21 | D28 | D56 | D84 | D112 | D140 | D168 | |
| Clinical Activity | Screen Days -21 to -2 | Check-in | Intervention Period | | | | | | | | | | | | Follow-up | | | | | | |

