Visit windows: Schedule Visits 01 through 15 with respect to Day 1. Visit 01 (-10 minutes for PK sample collection and vitals; -1 hour for ECG), Visit 01A (window for start of infusion \pm 10 minutes); Visits 01B and 01C (\pm 10 minutes); Visits 02, 03, 04, 05, 06 (\pm 6 hours), Visit 07 (\pm 12 hours); Visits 08, 09, 10 (\pm 2 days), and Visits 11, 12, 13, 14, and 15 (\pm 7 days).

Assessments should be done as close as possible to nominal time.

- 1 Day 1 = day of product administration. Day 1 evaluations prior to product administration will be considered as baseline for assessing subsequent AEs.
- 2 Day 10 outpatient visit is only applicable to 2 sentinel participants.
- 3 Height and weight will be measured and BMI will be calculated at Screening. Only weight will be measured at Check-in and Day 1

- 4 Vital signs will include body temperature, systolic and diastolic blood pressure, respiratory rate, and pulse. On Day 1, the vital signs and SPO₂ will be measured at predose, every 15 minutes from start of infusion for 2 hours, and at 4 hours and 8 hours postdose. For further details, refer to Section 8.1.2
- 5 A full physical examination will be performed at Screening (at minimum, assessment of skin, head, ears, eyes, nose, throat, neck, thyroid, lungs, heart, cardiovascular system, abdomen, lymph nodes, and musculoskeletal system/extremities). A brief physical examination (at minimum, assessment of skin, lungs, cardiovascular system, and abdomen [liver and spleen]) will be performed at Check-in, at Day 1 (pre-dose), at 8 hours, Day 10 (applicable only for 2 sentinel participants) and at ED visit. A brief physical examination will also be performed within 30 to 60 minutes of EOI. Interim physical examinations may be performed at the discretion of the investigator, if necessary, to evaluate AEs or clinical laboratory abnormalities.
- 6 A complete list of assessments is provided in Section 10.2.
- 7 Study product administration will be performed following predose activities.
- 8 The electrocardiogram (ECG) taken at Screening and on Day 1 before product administration will be a single reading; however, repeat ECGs are allowed at investigator's discretion to confirm the eligibility. Triplicate 12-lead ECGs will be obtained for all postdose time points. For Visit 01A, ECGs will be taken within 30 minutes of EOI.

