6.2. Study Product Administration

Subcutaneous Administration with rHuPH20

The SC administration site(s) to be used must be assessed as acceptable by the clinician and the participant. The preferred SC administration site is the abdomen. GSK3810109 will be mixed with rHuPH20 in the pharmacy and then administered via standard Medfusion 3500 syringe pump (or equivalent) in 1 infusion site at a rate of no more than 3 mL/minute. For Part 1, given the weight criterion in this study, the maximum volume needed to administer a 20 mg/kg SC dose is not expected to exceed 24 mL. **CCI** [REDACTED]

[REDACTED]. If the participant experiences side effects during the infusion, the rate of infusion may be slowed or stopped to alleviate the symptoms.

Intravenous Administration

For Part 2, participants will receive IV administration of GSK3810109. The IV access will be placed in an arm vein in an aseptic manner. A different site should be used for collection of PK blood samples; however, the same site may be used after flushing the line if another site is not available. GSK3810109 will be diluted with normal saline to infuse approximately 250 mL of solution at the appropriate concentration (as described in the current IB [[Investigator's Brochure](#)]) over about 60 minutes. The entire infusion should not exceed 2 hours. If the participant experiences side effects during the infusion, the rate of infusion may be slowed or interrupted to alleviate the symptoms.

There are no pre-medications for IV administration; however, based on emerging safety data from sentinel participants, these may be given at the investigator's discretion and in consultation with the Medical Monitor.

Study Product and Administration Regimen

GSK3810109 is a clear, colorless to yellow liquid, that is essentially free of visible particles; the product is supplied as a sterile aqueous buffered solution filled into 10 mL single-dose vials. Each vial contains a 6.25 ± 0.10 mL volume of GSK3810109 at a concentration of 100 ± 10 mg/mL in a formulation buffer composed of 10 mM sodium citrate, 50 mM sodium chloride, 150 mM arginine-hydrochloride, and 0.002%

polysorbate-80 at pH 6.5. Vials have a nominal fill volume of 6.25 mL to enable withdrawal up to 6.0 mL.

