6.6. Overdose

For this study, any administered dose of GSK3810109 and/or rHuPH20, greater than that intended for the study will be considered an overdose.

The investigator should use clinical judgment in treating overdose, as ViiV Healthcare is unable to recommend specific treatment other than supportive care.

In the event of an overdose, the investigator/treating physician should:

1. Contact the Medical Monitor immediately.
2. Monitor vital signs regularly for several hours after the overdose.
3. Closely monitor the participant for AE/SAE and laboratory abnormalities until GSK3810109 can no longer be detected systemically.
4. Obtain a sample for PK analysis from the date of the overdose of study intervention if requested by the Medical Monitor (determined on a case-by-case basis).
5. Document the quantity of the excess dose as well as the duration of the overdosing in the eCRF.

Since this is a single-dose administration of GSK3810109, dose modifications will not be applicable. However, if the participant experiences side effects during the infusion, the rate of infusion may be slowed or stopped to alleviate the symptoms.

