8.1.2. Vital Signs

- Vital signs will be measured in a supine position after the participant has been at rest for at least 5 minutes in a quiet setting without distractions (e.g., television, cell phones) and will include body temperature, systolic and diastolic blood pressure, respiratory rate, and pulse.
- For Part 1, on Day 1, the vital signs and SPO₂ will be measured at predose and at 4 hours and 8 hours postdose.
- For Part 2, on Day 1, the vital signs and SPO₂ will be measured at predose, every 15 minutes from start of infusion for 2 hours, and at 4 hours and 8 hours postdose.
- For Part 3, on Day 1, the vital signs and SPO₂ will be measured at predose and at 4 hours and 8 hours postdose.

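### Part 2: the 15-minute vital-sign and SpO2 series runs from the start of infusion, so close follow-up after the end of infusion shrinks from 60 minutes to none as the infusion lengthens to its 2-hour cap

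*Protocol*

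**What the plan says.** The Part 2 Schedule of Activities (Protocol 1.6, footnote 4) sets Day 1 vital signs and SpO2 at predose, "every 15 minutes from start of infusion for 2 hours, and at 4 hours and 8 hours postdose". Protocol 8.1.2 gives the same schedule ("every 15 minutes from start of infusion for 2 hours"). The vital-signs row has no entry in the EOI column, but footnote 4 governs the Day 1 times, so the blank does not by itself rule out a reading at that moment.

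The Synopsis describes the IV infusion as "expected to take approximately 60 minutes to administer; the entire infusion should not exceed 2 hours". On reactions during dosing, Protocol 6.2 says that "the rate of infusion may be slowed or interrupted to alleviate the symptoms", and Protocol 6.6 that "the rate of infusion may be slowed or stopped to alleviate the symptoms". No other reason for a longer infusion is given.

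Two Day 1 safety checks are timed from EOI: "For Visit 01A, ECGs will be taken within 30 minutes of EOI" (footnote 8) and "A brief physical examination will also be performed within 30 to 60 minutes of EOI" (footnote 5). The listed minimum content of the brief examination is skin, lungs, cardiovascular system and abdomen. It does not name blood pressure or SpO2.

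**The concern.** Because the series has a fixed start and a fixed length, close observation after EOI is whatever remains of the 2 hours. Infusion length is not independent of how the participant is doing: the stated trigger for slowing or interrupting is side effects. Among participants who complete the infusion, those with the longest infusions are therefore likely to be those who reacted, and they get the fewest close readings afterwards.

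The dose makes this worth a clause. The Synopsis says that no single dose above 40 mg/kg had been given to humans, and Protocol 8.2.6 lists infusion-related reactions, anaphylaxis and cytokine release syndrome (CRS) as events of special interest. Blood pressure and SpO2 are the direct measures of the hypotension and hypoxia that Protocol 2.3.1.1 names among severe reactions. What is at stake is individual safety cover and the completeness of the vital-sign record after a reaction.

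**Working it through.** The plan states no count of post-infusion readings, so there is no figure to reproduce. The check is a direct count.

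**Inputs.** Series times: 15, 30, ..., 120 minutes from the start, 8 readings (footnote 4; a reading at time 0 would not alter any count below). Later readings: 4 h and 8 h. Infusion length *D*: 60 minutes as planned, up to 120 at the cap (Synopsis; Protocol 6.2).

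**Formulas.**
- Strictly after EOI: number of series times greater than *D*.
- At or after EOI: number of series times at or above *D*.
- Day 1 total strictly after EOI: strict count + 2 (the 4 h and 8 h readings).
- Close cover after EOI: 120 − *D* minutes.
- Series end under the fix: the larger of 120 and *D* + 60. Extra readings: (series end − 120)/15.

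| *D* (min) | Strictly after EOI | At or after EOI | Day 1 total strictly after EOI | Close cover (min) | Series end under fix (min) | Extra readings |
|---|---|---|---|---|---|---|
| 60 | 4 | 5 | 6 | 60 | 120 | 0 |
| 75 | 3 | 4 | 5 | 45 | 135 | 1 |
| 90 | 2 | 3 | 4 | 30 | 150 | 2 |
| 105 | 1 | 2 | 3 | 15 | 165 | 3 |
| 120 | 0 | 1 | 2 | 0 | 180 | 4 |

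The loss between a 60-minute and a 120-minute infusion is four readings under either counting convention. The Day 1 totals do not depend on whether 4 h and 8 h are counted from the start or from EOI.

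**Gap at the cap.** The 120-minute reading falls at EOI. The Schedule's column header is "Time From Start of IV Infusion", so the 4 h reading comes 240 − 120 = 120 minutes after EOI. With the 10-minute window either way for Visit 01B, that is 230 − 120 = 110 to 250 − 120 = 130 minutes. If postdose were instead counted from EOI, the gap would be 240 minutes.

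**Infusions stopped early.** The direction reverses. Stopping at 20 minutes leaves 7 readings (30 to 120) and 120 − 20 = 100 minutes of cover. Stopping at 50 minutes leaves 5 readings (60 to 120) and 120 − 50 = 70 minutes.

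**Effect of the fix.** Any 60-minute stretch after EOI contains four multiples of 15, so every permitted infusion gets at least 4 close readings after EOI. For example, *D* = 100 gives 105, 120, 135 and 150. The most the fix could add is 8 × 4 = 32 readings, which would need all 8 infusions to reach the cap.

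**The case against.** The strongest reply is that the start of infusion is the right clock. Protocol 2.3.1.1 describes the timing of CRS and of most infusion-related events from the beginning of administration. On that clock every participant gets the same eight readings, and a longer infusion only means that more of them fall during dosing. The protocol sets no minimum vital-sign period after EOI, so the 60 minutes is a remainder (120 − 60), not a stated intention. This stands as a reason to keep the start anchor, and the fix keeps it. It does not supply a blood pressure or SpO2 reading between the end of a 2-hour infusion and 4 h.

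Existing safeguards are real. The triplicate ECG gives heart rate, participants stay until Day 8, and the risk table in Protocol 2.3.1 calls for close monitoring of systemic reactions. Two sentinels are dosed first, and timing may be changed on emerging data. In the first-in-human study, 4 of 14 IV participants had systemic symptoms, all mild and recovered within a day, although at 40 mg/kg or less. All this lowers the importance of the point. None of it guarantees the readings for the participant whose infusion is slowed, least of all a sentinel.

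A reader might infer more than the documents support:
- *Nothing is measured around EOI at the cap.* A full set falls due at EOI itself.
- *The series is defective because it ends while CRS is still possible.* That is equally true of a 60-minute infusion, to which the fix adds nothing. The case rests only on unequal follow-up after EOI.
- *Reacting participants always get less cover.* Those whose infusion is stopped early get more.
- *Discretionary readings would be lost to analysis.* SAP 4.1 leaves unscheduled visits out of summary tables but lists them and counts them in worst-case determinations. Whether extra readings during an in-clinic stay are visits at all is not stated, and SAP 4.3.1 lists all vital signs and SpO2.

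**Conclusion.** The point holds as a minor one. The scheduled 15-minute cover after EOI falls from 60 minutes to none across the permitted infusion lengths. At the cap there is then about 2 hours without a scheduled blood pressure or SpO2 reading.

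This rests on series readings at multiples of 15 minutes and on the 4 h reading being counted from the start, as the Schedule header has it. The link to reactions is an inference from the only stated reason for slowing, and it applies to completed infusions. The documents do not say how often infusions are slowed, so the number of participants affected is unknown and could be zero. Reactions would still be captured as adverse events, and no endpoint, estimand or test is affected.

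**What to change.** In Protocol 1.6 footnote 4 and in Section 8.1.2, keep the 15-minute interval and the start anchor, and replace the 2-hour limit with: *until the later of 2 hours from start or 60 minutes after end of infusion*. The 4 h and 8 h readings stay. The 60 minutes matches what a planned infusion already receives and ends with the existing post-EOI examination window.

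In SAP 4.3.1, state that readings after 120 minutes from this series are listed and count in any worst-case determination, but are not added as rows to the by-timepoint change-from-baseline summaries. Otherwise the tables would gain sparse rows at 135 to 180 minutes, filled only by participants with prolonged infusions.

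The cost is one clause in two places, one sentence in the SAP, and 0 to 4 routine readings per participant, all already in the clinic. A 60-minute infusion adds none.

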2. INTRODUCTION

Despite significant progress in the treatment and prevention of human immunodeficiency virus (HIV) infection, HIV/(acquired immunodeficiency syndrome) AIDS has remained a major global public health problem since the discovery of the virus in 1983. Reports by the Joint United Nations Programme on HIV/AIDS (UNAIDS) estimate that 79.3 million people have been infected with HIV since the start of the epidemic, contributing to 36.3 million deaths from AIDS-related illnesses [UNAIDS, 2021]. Despite these statistics, global incidences of new HIV infections have actually declined from peak rates in the mid-1990s; a reduction attributed in part to increased availability of antiretroviral therapy (ART) and the effective execution of prevention/treatment programs such as those that target mother-to-child transmission. Unfortunately, HIV infection is extremely complex and none of the current therapeutic regimens can cure an infection or induce a full recovery of the host immune system. Long-term toxicities, emergent and transmitted drug resistance, and drug-drug interactions create a continued unmet medical need for new antiretroviral medications (with new modes of action). Current approved treatment therapies require daily therapy. Thus, novel therapeutic strategies are being investigated.

The Vaccine Research Centre (VRC)/National Institute of Allergy and Infectious Diseases is investigating clinical applications of broadly neutralizing human monoclonal antibodies (bNAbs) that bind the HIV type 1 (HIV-1) envelope protein [Huang, 2016; Huang, 2012;

Kwon, 2012; Wu, 2010]. Such antibodies block infection of target cells in vitro and have been shown to prevent infection of non-human primates in in vivo models for HIV [Mascola, 2000; Pegu, 2014; Rudicell, 2014]. Through advances in B-cell immunology utilizing single-cell cloning methods, next-generation sequencing, high throughput computational analysis techniques, and increased cell culture survivability procedures, an extensive group of HIV-1 bNAbs have been isolated. These include an HIV-1 specific bNAb identified as N6 that was recently isolated from a patient with a 21-year known history of HIV-1 infection that was controlled in the absence of ART [Huang, 2016].

In order to improve the pharmacokinetics (PK) of N6, 2 amino acid substitutions (methionine to leucine and an asparagine to serine M428L/N434S, that collectively yielded N6LS [GSK3810109]) were introduced within the C-terminus of the heavy chain constant region of N6 via site-directed mutagenesis to increase its binding affinity for the neonatal Fc-receptor (FcRn). This modification results in enhanced recirculation and longer plasma half-life of GSK3810109 relative to the wild-type Ab.

GSK3810109 is being developed for the prevention of HIV-1 infection in uninfected adults and for treatment of HIV-1 infection in infected adults. The first-time-in-human (FTIH) study (VRC 609) is currently ongoing to evaluate the safety, tolerability, and PK of this antibody.

2.1. Study Rationale

GSK3810109 (identified as N6LS and VRC-HIVMAB091-00-AB in scientific reports), is a highly potent and broadly neutralizing monoclonal antibody directed against the CD4-binding site of the HIV-1 envelope glycoprotein 120 subunit (gp120). GSK3810109 can mediate extraordinary breadth and potency against various HIV isolates, including strains traditionally resistant to other antibodies in this class.

This study is designed to evaluate safety, tolerability, and PK endpoints in healthy adult participants, when GSK3810109 is administered as either subcutaneous (SC) injection (Part 1 and Part 3 of study) or by intravenous (IV) infusion (Part 2 of study). Dosing by either SC or IV infusion may each offer practical advantages related to tolerability, simplicity, or frequency of dosing in the administration of GSK3810109. The inclusion of both routes of administration in this study is an efficient design to enable rapid progression to future studies using either 1 or both routes of administration.

This current study is aimed at investigating options that may reduce the frequency of administration and thus the burden on patients by evaluating the feasibility of a high dose of GSK3810109 administered IV, and larger SC dose volumes (>2.5 mL) of GSK3810109 using a 20 mg/kg or [CC]

In this study, an IV dose of 60 mg/kg of GSK3810109 will be administered, which may offer the potential for an ultra-long-acting target profile to support administration every 4 to 6 months, thus improving adherence. Medication adherence and decreasing frequency of clinic visits is the most important determinant for sustained viral suppression and long-term treatment success.

The rHuPH20 enzyme facilitates the SC delivery of co-administered therapeutics. Hyaluronidase injection is effective for the use as an adjunct to increase the absorption and dispersion of other injected drugs; for hypodermoclysis; as an adjunct in SC urography for improving the resorption of radiopaque agents (United States Federal Register [23 September 1970]).

The FTIH Protocol VRC 609 study is currently ongoing to evaluate the safety, tolerability, and PK of GSK3810109 (N6LS). As of 4 August 2021, no significant safety findings were noted. Two Grade 3 events of injection site erythema, one after receiving 5 mg/kg SC N6LS + 2000 U rHuPH20/mL and one after receiving 20 mg/kg SC N6LS + 2000 U rHuPH20/mL, were noted; however, the Grade 3 erythema observed in both individuals was well tolerated and judged to not represent an increased safety risk for study participants.

